5.5.3 Laboratory Values

Laboratory results will be summarized using International System of Units, as appropriate. For all quantitative parameters, the actual value and the change from baseline to each postbaseline visit and to the end of treatment (defined as the last on-treatment value) will be summarized by visit and treatment group using descriptive statistics. Qualitative parameters will be summarized using frequencies (number and percentage of subjects), and changes from baseline to each postbaseline visit and to end of treatment will be reported using shift tables. Percentages will be based on the number of subjects with both nonmissing baseline and relevant postbaseline results.

Laboratory test results will be assigned a low/normal/high (LNH) classification according to whether the value was below (L), within (N), or above (H) the laboratory parameter's reference range. Within-treatment comparisons for each laboratory parameter will be based on 3-by-3 tables (shift tables) that compare the baseline LNH classification to the LNH classification at each postbaseline visit and at the end of treatment. Similar shift tables will also compare the baseline LNH classification to the LNH classification for the highest and lowest value during the treatment period.

[Section 12.1](#) (Sponsor's Grading for Laboratory Values) presents the criteria that will be used to identify subjects with treatment-emergent markedly abnormal laboratory values (TEMAVs). Except for phosphate, a TEMAV is defined as a postbaseline value with an increase from baseline to a Grade of 2 or higher. For phosphate, a TEMAV was defined as a postbaseline value with an increase from baseline to a Grade of 3 or higher. When displaying the incidence of TEMAVs, each subject may be counted once in the laboratory parameter high and in the laboratory parameter low categories, as applicable.

5.5.4 Vital Signs

Descriptive statistics for vital signs parameters (ie, systolic and diastolic BP, pulse, respiratory rate, temperature, weight), and changes from baseline will be presented by visit and treatment group.

In addition, frequency counts of clinically notable vital signs will be summarized by treatment group. Table 3 presents the clinical notable ranges.

Table 1. Clinical Notable Ranges for Vital Signs

Vital Sign	Criterion for Low	Criterion for High
Pulse (bpm)	< 50	> 100
Temperature (°C)	< 36	> 38
Weight (kg)	< 45	> 100
Systolic BP	< 90	> 160
Diastolic BP	< 50	> 100

5.5.5 Electrocardiograms

Descriptive statistics for ECG parameters and changes from baseline will be presented by visit and treatment group. Shift tables will present changes from baseline in ECG interpretation (categorized as normal; abnormal, not clinically significant; and abnormal, clinically significant) to the end of treatment.

In addition, the number (percentage) of subjects with at least 1 post-baseline abnormal ECG result in QTcF during the treatment period will be summarized. Clinically abnormal ECG results in QTcF will be categorized as follows:

Absolute QTc interval prolongation:

- QTc interval >450 msec
- QTc interval >480 msec
- QTc interval >500 msec

Change from baseline in QTc interval:

- QTc interval increases from baseline >30 msec

- QTc interval increases from baseline >60 msec

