5.5 SAFETY ANALYSES

Evaluations of safety will be performed on the Safety Analysis Set. The incidence of AEs, out-of-normal-range laboratory safety test variables, abnormal electrodiagram (ECG) findings, out-of-range vital signs, safety MRI findings, suicidality, results of the sleep questionnaire, ADAS-cog Reliable Change Index (RCI) Alert triggered, dermatology findings, and neurological examination along with change from baseline in laboratory safety test variables, ECGs, and vital sign measurements will be summarized by treatment group.

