5.5.3 Laboratory Values

Laboratory results will be summarized using International System of Units, as appropriate. For all quantitative parameters, the actual value and the change from baseline to each postbaseline visit and to the end of treatment visit and 12 week Follow-up visit will be summarized by visit and treatment group using descriptive statistics. Qualitative parameters will be summarized using frequencies (number and percentage of subjects), and changes from baseline to each postbaseline visit and to end of treatment visit and 12 week Follow-up visit will be reported using shift tables. Percentages will be based on the number of subjects with both nonmissing baseline and relevant postbaseline results.

Laboratory test results will be assigned a low/normal/high (LNH) classification according to whether the value was below (L), within (N), or above (H) the laboratory parameter's reference range. Within-treatment comparisons for each laboratory parameter will be based on 3-by-3 tables (shift tables) that compare the baseline LNH classification to the LNH classification at each postbaseline visit and at the end of treatment visit and 12 week Follow-up visit. Similar shift tables will also compare the baseline LNH classification to the LNH classification for the highest and lowest value during the treatment period.

[Section 12.1](#) (Sponsor's Grading for Laboratory Values) presents the criteria that will be used to identify subjects with treatment-emergent markedly abnormal laboratory values (TEMAVs). Except for phosphate, a TEMAV is defined as a postbaseline value with an increase from baseline to a Grade of 2 or higher. For phosphate, a TEMAV was defined as a postbaseline

value with an increase from baseline to a Grade of 3 or higher. When displaying the incidence of TEMAVs, each subject may be counted once in the laboratory parameter high and in the laboratory parameter low categories, as applicable.

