5.5.5 Electrocardiograms

Descriptive statistics for ECG parameters and changes from baseline will be presented by visit and treatment group. Shift tables will present changes from baseline in ECG interpretation (categorized as normal; abnormal, not clinically significant; and abnormal, clinically significant) to the end of treatment visit and 12 week Follow-up visit.

In addition, the number (percentage) of subjects with at least 1 post-baseline abnormal ECG result in corrected QT interval calculated using Fridericia's formula (QTcF) interval during the treatment period will be summarized. Clinically abnormal ECG results in QTcF interval will be categorized as follows:

Absolute QTcF interval prolongation:

- QTcF interval >450 msec
- QTcF interval >480 msec
- QTcF interval >500 msec

Change from baseline in QTcF interval:

- QTcF interval increases from baseline >30 msec
- QTcF interval increases from baseline >60 msec

Combined:

- QTcF interval >450 msec and QTcF interval increases from baseline >60 msec

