5.5 SAFETY ANALYSES

Evaluations of safety will be performed on the Safety Analysis Set. The incidence of AEs, out-of-normal-range laboratory safety test variables, abnormal ECG findings, and out-of-range vital signs, suicidality, results of the sleep questionnaire, along with change from baseline in laboratory safety test variables, ECGs, and vital sign measurements will be summarized by treatment group.

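### The overall ECG reading is tabulated only at end of treatment and follow-up, so section 5.5.5 only partly delivers the incidence of abnormal ECG findings promised in 5.5

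*SAP*

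**What the plan says.** SAP v2.0 (19 March 2020) is the current plan for both studies. Section 5.5 lists what will be summarised by treatment group, beginning "The incidence of AEs, out-of-normal-range laboratory safety test variables, abnormal electrodiagram (ECG) findings".

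Section 5.5.5 then specifies three ECG outputs:

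- descriptive statistics of ECG parameters and their changes from baseline, by visit and arm;
- shift tables of the overall reading, that is, "changes from baseline in ECG interpretation (categorized as normal; abnormal, not clinically significant; and abnormal, clinically significant) to the end of treatment", where the v2.0 sentence continues so that the full set of time points is "to the end of treatment visit and 12 week Follow-up visit";
- the number and percentage of "subjects with at least 1 post-baseline abnormal ECG result in corrected QT interval" during the treatment period, in six QTcF categories (above 450, 480 and 500 msec; increases above 30 and 60 msec; and one combination).

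Section 8.2 defines end of treatment as a single assessment: the earliest one on or after the last dose, within a 56-day limit. It also defines a separate last-on-treatment visit, which 5.5.5 does not use.

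For laboratory values, 5.5.3 plans shifts to every post-baseline visit and adds: "Similar shift tables will also compare the baseline LNH classification to the LNH classification for the highest and lowest value during the treatment period". For white matter disease on safety MRI, 5.5.6 plans shifts to each visit as well as to end of treatment and follow-up.

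The two v1.0 plans of 17 March 2017 also promise the incidence of abnormal ECG findings, and they shift the ECG reading to end of treatment only. Version 2.0 added the follow-up visit and left the rest of that sentence alone.

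**The concern.** Incidence counts every subject in whom a finding occurs during treatment. A shift to one assessment at the end gives the prevalence at that moment. The two agree for abnormalities that persist and diverge for those that resolve, whether spontaneously or after treatment.

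If the overall reading is summarised only at end of treatment and follow-up, a disturbance of rhythm or conduction that was read as clinically significant mid-study and later cleared leaves no trace in the reading tables. An imbalance between arms made up of such events could be missed there. Safety is a main output of this report: in September 2019 the DSMB recommended stopping because risk outweighed benefit, and it described a worse adverse event profile on active drug.

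**Working it through.** No arithmetic applies to the main point. It is settled by setting the specified outputs side by side (all SAP v2.0).

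| Measure | Shift or category at each on-treatment visit | Worst value or any-time count | End of treatment and follow-up |
|---|---|---|---|
| Laboratory values (5.5.3) | yes | yes (highest and lowest) | yes |
| MRI white matter disease (5.5.6) | yes | not specified | yes |
| QTcF thresholds (5.5.5) | not specified | yes | not specified |
| Overall ECG reading (5.5.5) | not specified | not specified | yes |

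Only the last row has neither by-visit nor any-time coverage during treatment.

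Next, follow one subject through the outputs. The baseline reading is normal. At a mid-treatment visit the ECG shows an abnormality other than QTcF prolongation and is read as clinically significant. By the first ECG on or after the last dose the reading is normal again.

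1. By-visit statistics: the subject contributes numeric values to a mean. I take this output to be numeric because it includes changes from baseline and because the reading has its own sentence. Nothing is counted as abnormal.
2. Shift table: under the 8.2 definition the mid-treatment ECG cannot supply the end-of-treatment cell. The subject is shown as normal to normal.
3. QTcF count: no threshold was crossed, so the subject is not counted.
4. Adverse event tables (5.5.2): the subject is counted if the finding was reported as an adverse event, and otherwise not. This SAP does not say that a clinically significant ECG must be reported as one.

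So none of the three outputs in 5.5.5 records this subject as having had an abnormal ECG.

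On size: among subjects with a clinically significant reading at any on-treatment visit, the share visible in the end-of-treatment table equals the share whose reading is still in that category at the end-of-treatment assessment. This can lie anywhere from none to all. The SAP gives no ECG schedule, abnormality rate or persistence from which to narrow it.

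**The case against.** The best case for the plan has four parts.

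- **ECG abnormalities are counted elsewhere.** A reader might infer that a mid-treatment clinically significant ECG is counted nowhere. The SAP does not support that. QTcF exceedances at any post-baseline visit are counted, and an abnormality reported as an adverse event enters the treatment-emergent tables, including those for events leading to discontinuation, interruption or concomitant treatment. For a subject who stops drug because of an ECG finding, the end-of-treatment cell takes the first ECG on or after stopping. All of this stands and limits the point to readings other than QTcF that had resolved.
- **Section 5.5 is an overview.** It does not say that every category of the reading will be counted at any time, and the QTcF count is an incidence of an abnormal ECG result. That is fair, so I call the promise partly delivered and do not call it contradicted. QTcF alone is still a narrow rendering of "abnormal electrodiagram (ECG) findings".
- **The table shells are in a separate document (section 11).** They may contain a by-visit reading table. This cannot be checked, and 5.5.5 does not call for one.
- **Any figure for the loss is assumed.** If each abnormality appeared at exactly one of 6 to 10 on-treatment ECGs, at random, the last ECG would show 1/10 to 1/6 of them (10% to 17%). A reader might take that as the size of the problem. The number of ECGs and the complete lack of persistence are both assumptions outside the SAP, and zero persistence is the extreme case. A contrast of p-values would be further from the plan, because 5.5.5 is descriptive and both studies stopped short of the planned 950 per arm.

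**Conclusion.** The point holds in a limited form. In SAP v2.0, section 5.5.5, the overall ECG reading is summarised only at end of treatment and at the 12-week follow-up, and the only any-time ECG incidence is for QTcF. A clinically significant reading of another kind that had resolved by end of treatment appears in no ECG interpretation summary specified there, so the incidence announced in 5.5 is only partly delivered. The plan treats laboratory values more fully.

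This is a minor gap in safety reporting. It does not touch the primary, secondary or any other efficacy analysis. Its size cannot be stated from the SAP. The conclusion rests on the text of 5.5.5 and on the 8.2 definition of end of treatment, and it assumes that the separate shells do not already add the missing table.

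**What to change.** In SAP v2.0, section 5.5.5, add:

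- a shift table from the baseline ECG reading to the worst on-treatment reading, with clinically significant abnormality as the worst of the three levels;
- by arm, the number and percentage of subjects who worsen from baseline to the clinically significant category at any on-treatment visit, with unscheduled ECGs included.

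State the window, for example from first to last dose. For the denominator, use subjects with a baseline reading and at least one on-treatment reading, as 5.5.3 does for laboratory percentages. Keep the end-of-treatment and follow-up shifts, which answer a different question.

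The cost is a sentence or two in the SAP and one extra descriptive table built from the same ECG readings. No new test or multiplicity adjustment is needed. If the shells already contain such a table, 5.5.5 need only say so.

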5.5.6 C-SSRS

The C-SSRS responses will be mapped to C-CASA. The incidence of new or worsening suicidal ideation or suicidal behavior will be summarized by treatment group. Continuous variables will be summarized by descriptive statistics; number of subjects, mean, standard deviation, median, minimum, and maximum and categorical variables by number (percentage) of subjects.

5.5.7 Other Safety Analyses

Cognitive decline will be assessed as a safety assessment, in addition to efficacy assessments. Cognitive assessments will include the ADAS-cog₁₄, MMSE, and CDR.

vMRI will be used to evaluate disease modification as indicated by measurements of brain atrophy. A large number of studies, including the AD Neuroimaging Initiative, have shown that quantitative measurements of hippocampal, whole brain, and total ventricular volume provide robust and reliable biomarkers of disease progression, and potential for assessment of PD efficacy.

MRI sequences will be collected for all subjects at 12 and 24 months per the Schedule of Assessments. vMRI data will be analyzed at the Screening Visit and at Visits 9 and 13 (12 and 24 months of treatment). QC and normalization procedures for measurements of the whole brain, total ventricular volume, and right and left hippocampal volumes will be based on a validated algorithm and conducted in the same central laboratory. Additional analysis of regions of interest and cortical thickness may also be performed.

5.6 Pharmacokinetic, Pharmacodynamic, and PHARMACOGENOMIC/PHARMACOGENETIC ANALYSES

Pharmacokinetic Analyses

The PK Analysis Set will be used for the summaries of elenbecestat (E2609) plasma and CSF concentrations.

A population PK approach will be used to characterize the PK of elenbecestat (E2609). The effect of covariates (ie, demographics) on elenbecestat (E2609) PK will be evaluated. The PK model will be parameterized for clearance (CL) and volumes of distribution. Derived exposure parameters such as AUC will be calculated from the model using the individual posterior estimate of CL and dosing history.

Pharmacokinetic - Pharmacodynamic Analyses

The PK/PD relationship between CSF biomarker levels and plasma PK parameters or CSF concentrations of elenbecestat (E2609) will be explored graphically and any emergent relationship will be explored through population PK/PD modeling. These PK parameters include

maximum observed concentration (C_{\max}), and $AUC_{(0-24)}$ derived from the population PK model. The PK/PD relationship between plasma PK parameters and CSF concentrations of elenbecestat (E2609) with other biomarkers may also be explored using similar methods.

Additionally, the relationship between various PK parameters (eg, C_{\max}) or CSF concentrations of elenbecestat (E2609) and CDR scores (CDR-SB, CDR global score, and CDR Memory Box score) at 24 months (including both absolute score and the change from baseline), and the relationship between various PK exposure parameters or CSF concentrations of elenbecestat (E2609) and the change from Baseline for 24 months in ADAS-cog₁₄, and the MMSE, will be explored graphically. Any emergent relationships will be explored through population PK/PD modeling. The relationship between exposure to elenbecestat (E2609) and most frequent AEs will also be explored.

Details of further analyses of pharmacokinetic/pharmacodynamic data will be described in a separate PK/PD analysis plan.

5.7 OTHER ANALYSES

No other analyses are planned.

6 INTERIM ANALYSIS

There is no interim analysis of efficacy, but there will be a futility analysis when 30% subjects have completed 24 months. The sponsor may stop the trial for futility with nonbinding futility boundary calculated using conservative O'Brien-Fleming boundary of Lan-DeMets alpha spending function with 30% information based on completers. If the actual percent information of the futility analysis is different from 30%, the futility boundary will be recalculated using the actual percent information at time of futility analysis. A blinded sample size re-estimation through estimated standard deviation based on blinded data prior to the completion of enrollment, will be performed if there is an indication that sample size assumptions need to be changed. This blinded sample size re-estimation could be performed based on signals from external studies or based on review of blinded data from this study prior to completion of enrollment. The standard deviation of the primary endpoint was estimated based on data from the ADNI study. It is possible that the standard deviation for the same endpoint in clinical trials may be larger than that from this observation study.

An independent DSMB will convene at regular intervals to monitor the overall safety of the study and to make recommendations to the sponsor related to study safety as appropriate. The DSMB will be asked to review the cumulative safety data up to the date identified to make a determination if the trial is safe to proceed unchanged or to provide recommendations to the Sponsor as to how to proceed. The study will proceed, including randomization of additional subjects, during DSMB safety reviews. DSMB reviews will then continue to occur at regular intervals. Details will be provided in the DSMB Charter.

7 DEFINITIONS AND CONVENTIONS FOR DATA HANDLING

7.1 DEFINITION OF BASELINE

The baseline value for efficacy, biomarker and safety will be defined as data collected prior to and/or on the date of first dose, usually the same day as the Day 1 (Visit 2). If there is more than one value on or before Day 1, the value closest to and prior to (including on) the date of first dose will be used as the baseline value.

7.2 ALGORITHMS FOR EFFICACY PARAMETERS

This section describes the algorithms and missing data handling procedure to derive the totals scores for the efficacy parameters: CDR, ADAS-Cog₁₄, MMSE, and FAQ.

CDR: The CDR is a clinical global rating scale requiring the interviewing of both the subject and an informant who knows and has contact with the subject. The CDR is a clinician-directed assessment of both cognition and function, and is intended to capture the state and therefore the disease stage of the individual. The CDR assesses 6 domains of subject function; memory, orientation, judgment and problem solving, community affairs, home and hobbies, and personal care. Each of these items has a maximum possible score of 3 points and the total score is a sum of the item scores (sum of boxes) giving a total possible score of 0 to 18 with higher scores indicating more impairment.

ADAS-cog₁₄: The ADAS-cog is the most widely used cognitive scale in AD clinical studies. The 14-item version (as shown in Table 4) is considered more sensitive for less impaired populations such as MCI/Prodromal and mild AD subjects.

Table 2. ADAS-cog₁₄ Items and Algorithm for Derivation of Item Scores and Total Score

Item	Algorithm	Handling Missing Data	Score Range
1. Word Recall	Total the number of “No” responses for each trial. The subscore is the sum the scores from trials 1, 2, and 3, divide by 3.	If a trial is missing or partially done then trial score is missing. If a trial score is missing then the subscore is missing	0 to 10
2. Commands	Total the number of “No” responses from the 5 tasks	If any task is missing then the subscore is missing	0 to 5
3. Constructional Praxis	Count the number of “No” responses. The subscore is	If any task is missing then the subscore is missing	0 to 5

	0 = all 4 drawings correct 1= 1 figure drawn incorrectly 2= 2 figures drawn incorrectly 3= 3 figures drawn incorrectly 4= 4 figures drawn incorrectly 5= no figures drawn, scribbles, parts of forms		
4. Delayed Word-Recall	Total the number of "No" responses.	If any response is missing then subscore is missing	0 to 10
5. Naming Objects / Fingers	Total the number of "No" responses. The subscore is 0= 0-2 "no" responses 1= 3-5 "no" responses 2= 6-8 "no" responses 3= 9-11 "no" responses 4= 12-14 "no" responses 5= 15-17 "no" responses	If any response is missing then subscore is missing	0 to 5
6. Ideational Praxis	Total the number of "No" responses.	If any response is missing then subscore is missing	0 to 5
7. Orientation	Total the number of "No" responses.	If any response is missing then subscore is missing	0 to 8
8. Word Recognition	For each trial, total the number of "1" responses. If the total is 12 or less, then the trial score = total. If the total is > 12 then trial score=12. The subscore is the sum the scores from trials 1, 2, and 3, divide by 3.	If a trial is missing or partially done then trial score is missing. If a trial score is missing then the subscore is missing	0 to 12
9. Remembering Test Instructions	The subscore is 0= None, 1= Very Mild, 2= Mild, 3= Moderate, 4= Moderately Severe, 5= Severe	If the response is missing then subscore is missing	0 to 5
10. Comprehension	The subscore is 0= None, 1= Very Mild, 2= Mild, 3= Moderate, 4= Moderately Severe, 5= Severe	If the response is missing then subscore is missing	0 to 5
11. Word Finding Difficulty	The subscore is 0= None, 1= Very Mild, 2= Mild, 3= Moderate, 4= Moderately Severe, 5= Severe	If the response is missing then subscore is missing	0 to 5
12. Spoken Language Ability	The subscore is 0= None, 1= Very Mild, 2= Mild, 3= Moderate, 4= Moderately Severe, 5= Severe	If the response is missing then subscore is missing	0 to 5
13. Executive Function (Maze)	The subscore is based on the total number of seconds to complete the task and/or whenever the task was stopped due to 2 errors being made, as follows; 0 = 0-30 seconds 1 = 31-60 seconds 2 = 61 – 90 seconds 3 = 91 – 120 seconds 4 = 121-239 seconds	If the response is missing then the subscore is missing	0 to 5

	5 = 240 seconds or at least 2 errors																
14. Number Cancellation	Adjusted Score = Total # correct targets crossed off minus Total # incorrect targets crossed off minus Total # times reminded of task. Then use Adjusted Score to determine the subscore as follows; 
 
 Adjusted Score	Subscore	
 
 ≥23	= 0	
 
 18-22	= 1	
 
 13-17	= 2	
 
 9-12	= 3	
 
 5-8	= 4	
 
 ≤4	= 5	
 
	Adjusted Score	Subscore	≥23	= 0	18-22	= 1	13-17	= 2	9-12	= 3	5-8	= 4	≤4	= 5	If any component of the adjusted score is missing then the subscore is missing	0 to 5
Adjusted Score	Subscore																
≥23	= 0																
18-22	= 1																
13-17	= 2																
9-12	= 3																
5-8	= 4																
≤4	= 5																
Total Score	Total Score = sum of the subscores above	If any subscore is missing then Total Score is missing	0 to 90														

MMSE: The MMSE is a cognitive instrument commonly used for screening purposes, for staging of disease severity and is often measured longitudinally in AD clinical studies to follow disease progression and treatment effects. MMSE is composed of 30 questions group into domains. For each of the MMSE domains add the correct responses. If a domain has missing data then the domain is missing. From the domains, one can compute the six items as show in Table 5. If any domain is missing then the item is missing. The MMSE Total Score (range 0 to 30) = sum of the six items. If any item score is missing then the Total Score is missing.

Table 3. MMSE Domains and Items

Domain	Score Range	Item	Score Range
1. Orientation to Time	0 to 5	1. Orientation to Time	0 to 5
2. Orientation to Place	0 to 5	2. Orientation to Place	0 to 5
3. Registration	0 to 3	3. Registration	0 to 3
4. Attention and Calculation ^a	0 to 5	4. Attention and Calculation	0 to 5
5. Recall	0 to 3	5. Recall	0 to 3
6. Naming	0 to 2	6. Language (Sum of Naming, Repetition, Comprehension, Reading, Writing, and Drawing)	0 to 9
7. Repetition	0 to 1		
8. Comprehension	0 to 3		
9. Reading	0 to 1		
10. Writing	0 to 1		
11. Drawing	0 to 1		
		Total Score	0 to 30

^a Spell WORD Forward, then Backward score is only use if Attention and Calculation score is not available

FAQ: The FAQ is composed of 10 activities. Each activity is rated as 0 = Normal, 1 = Has difficulty but does by self, 2 = Requires assistance, 3 = Dependent, 8 = Not Applicable. The Total Score is the sum of the 10 activity. If any activity is missing then the Total Score is missing. Activities marked as “Not Applicable”, are not use in the computation of the Total Score. However, in order to account for “Not Applicable” activity(s), the Total Score is weighted as follows;

Total Score = Total Score x 30 / (30 minus 3 times the number of activities marked “Not Applicable”)

